users (n = 5), and 1 group for substance users (n = 9). The interventionist will follow the intervention manual to deliver the intervention and assign homework for group members to practice on their own. In the following sessions, the interventionist will review progress with participants, guide participants through exercises, and identify additional problems to be addressed in subsequent sessions.

3.5.4.2.3 Fidelity check: To ensure intervention fidelity, all the intervention sessions will be audio-recorded and interventionists' progress notes will be reviewed for supervision purposes; in addition, subsequent analysis of interventionists' reliability will be conducted. At the end of each month, the Thai-speaking researchers and the team will randomly select and review 20% of the recordings and progress notes throughout the study period. The research staff will host biweekly supervision sessions for the interventionists to discuss difficult cases, including their intervention decisions. Finally, the PIs ([name] and [name]) will travel to the study site at least twice a year to provide oversight to the research personnel. The PIs will also be available daily through online communication with the research personnel for immediate troubleshooting to ensure smooth research operations. Drs. [name], [name], and [name] will meet regularly and frequently online to review progress, solve emerging issues during project operations, and revise the plans for action.

3.5.4.2.4 To minimize attrition, we will implement specific procedures beginning at baseline. The procedures, which we successfully employed in prior projects, include verifying contact information at each assessment, obtaining any potential upcoming changes in addresses every month, using potential friend and family locators, collecting email addresses, and sending cards when approaching follow-up dates. Based on our prior experiences, we expect that attrition will be lower than 15% with application of these procedures. Therefore, we aim to recruit $80/(1-0.15) = 94$ participants at our baseline, which after attrition may result in a sample of 80 for analysis.

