3.5.4.2.8.2 To evaluate preliminary efficacy: Our study design involves a two-group randomized-controlled clinical trial with four assessments for each participant and a total of 320 observations. **The study is not fully powered for efficacy, limiting the sophistication of the analyses we can conduct to test efficacy.** However, to obtain robust estimations, we will take the following steps: (a) we will examine the scope and mechanisms for missing data and attrition to investigate the extent to which the missing-at-random (MAR) assumption is violated, and, if it is violated, we will adapt procedures recommended by Barnes et al.;¹⁵¹ (b) we will examine all measures at each observation time using univariate statistics to identify potential irregular response patterns and determine overall quality of data; (c) we will assess scale reliability and compare it to published psychometrics in comparable populations; (d) we will triangulate objective and self-report measurement of adherence; (e) we will give special attention to our key primary outcome variables (quality of life and objective health measures) as well as secondary outcome variables (stigma, disclosure preparedness, family relations, family support, self-management efficacy, adherence, depressive and anxiety symptoms, and physical symptoms; note that all the outcomes are continuous); and (f) we will investigate the quality of random assignment by conducting a series of bivariate statistics comparing selected demographic, clinical, and psychosocial factors between treatment groups at baseline. Important findings may result in the modification of subsequent analyses.

[figure not shown]
We will use Generalized Estimating Equations (GEE) to test the proposed hypotheses while controlling for stratification and basic demographic backgrounds. This GEE framework allows us to carry out statistical tests for all the major hypotheses by comparing "population averages" between groups while appropriately adjusting for autocorrelations in observations due to repeated measures for the same groups of participants. We will further apply the small-sample estimator of variance to accommodate our sample size.¹⁵² To compute

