standard errors and confidence intervals for statistical inferences, we will use a clustered sandwich estimator to obtain robust estimations. Note that, for simplicity of the exposition, controlling variables are not shown in the equations. All the statistical testing will be analyzed with the statistical software packages Stata and R. **Please note, our interpretations will focus on the size of the between-group effect and its replication in the DT group because this study is not designed to have power to detect small effects.**

We will fit the following GEE intent-to-treat model with the Thai

PLWH: $g(E(Y_{it})) = \beta_{01} + \beta_{02} * Week_{i4} + \beta_{03} * Week_{i7} + \beta_{04} * Week_{i10} + \beta_{05} * I(ET_i) + \beta_{06} * I(ET_i) * Week_{i4} + \beta_{07} * I(ET_i) * Week_{i7} + \beta_{08} * I(ET_i) * Week_{i10}$ where $g(\cdot)$ denotes a proper link function; Y_{it} denotes primary or secondary outcomes in separate models for participant i at Week t ; $t = 1, 4, 7$, and 10 ; and $I(ET_i)$ denotes a binary variable indicating whether participant i belongs to the immediate treatment group. In this model, β_{01} represents the mean

outcome levels for DT at Week 1; β_{02} represents the slope for TAU between Week 1 and Week 4; β_{03} represents the slope for DT between Week 1 and Week 7; β_{04} represents the slope for TAU between Week 1 and Week 10; β_{05} represents the average group difference in outcomes between TAU and ET groups at Week 1; β_{06} represents the average group difference in the slope between TAU and ET groups between Week 1 and Week 4; β_{07} represents the average group difference in the slope between TAU and ET groups between Week 1 and Week 7; and β_{08} represents the average group difference in the slope between TAU and ET groups between Week 1 and Week 10. We define that the main between-group treatment effect is equal to β_{06} ; therefore, we expect that β_{06} will be significantly different from 0.

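### The missing-data step acts only if MAR is judged violated, which the data cannot show, and names no MAR-valid default, so β06 may be biased if outcome-dependent dropout differs by arm

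*Combined protocol and SAP*

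**What the plan says.** Analytic handling of missing data rests on step (a) of section 3.5.4.2.8.2. The team will look at how much is missing and why, "investigate the extent to which the missing-at-random (MAR) assumption is violated", and "if it is violated, we will adapt procedures recommended by Barnes et al". The plan gives no criterion for a violation, does not describe the cited procedures, and does not say what is done if MAR is taken to hold.

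The analysis itself is stated as: "We will use Generalized Estimating Equations (GEE) to test the proposed hypotheses while controlling for stratification and basic demographic backgrounds". GEE is described as "appropriately adjusting for autocorrelations in observations due to repeated measures for the same groups of participants", but no working correlation is named. For inference, "we will use a clustered sandwich estimator to obtain robust estimations", with a small-sample variance correction. The model is labelled intent-to-treat, without saying how a participant with no Week 4 value contributes. The main effect is β06, the ET–TAU difference in change from Week 1 to Week 4. Weighting, imputation, a likelihood-based model and a missing-data sensitivity analysis are not mentioned.

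On extent, section 3.5.4.2.4 says "we expect that attrition will be lower than 15" per cent, and recruits 94 to leave 80.

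**The concern.** There are two faults of principle.

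1. **The trigger cannot be operated.** Observed data can speak against MCAR, for example if dropouts had higher baseline stigma. They cannot separate MAR from MNAR, because that depends on the values not seen.
2. **The threshold is the wrong one for this model.** Unweighted GEE on available visits is guaranteed only under MCAR, or when dropout is explained by covariates in the model. The Week 1 score enters the model as an outcome, not as a covariate. If dropout depends on it, MAR holds, step (a) prescribes nothing, and β06 can still be biased.

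The stated safeguards do not fill the gap. The sandwich and small-sample variances concern the standard error, not the estimate. Recruiting 94 protects precision.

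The design gives a reason for dropout to work differently by arm. Only ET has four 120-minute group sessions, and its Week 4 assessment comes straight after the fourth (3.5.4.2.7). The estimate also has a later use: section 3.5.4.3 takes the effect sizes from this trial to set the sample size of the next study.

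**Working it through.** **Plan's own figures.** 80/(1 − 0.15) = 94.1, which agrees with the stated 94. The detectable 2.4 at 80% power cannot be reproduced, because the alpha, SD and correlation are not in the text. It can only be solved backwards.

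**Scale (assumed: two-sided 5%, 40 per arm, within-person correlation ρ = 0.6).**
- Implied SE of β06: 2.4/(1.960 + 0.842) = 0.857.
- SD of the Week 1–4 change: 0.857/√(2/40) = 3.83.
- SD of the score: 3.83/√(2(1 − 0.6)) = 4.28, so 2.4 is 2.4/4.28 = 0.56 SD.

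**Bias with an independence working correlation.** With a full set of arm-by-week terms, this fit returns the observed mean at each visit. Week 1 is complete; Week 4 is the mean of those who stay. If dropout depends on the standardised baseline Z, the bias in one arm is

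ρ × SD × E(Z | stayed).

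The bias in β06 is the ET value minus the TAU value. For logistic dropout with 15% lost by Week 4, numerical integration gives E(Z | stayed) = −0.098 at an odds ratio of 2 per SD (intercept −1.893) and −0.142 at 3 (intercept −2.105).

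| Dropout depends on baseline | OR 2 | OR 3 | Share of 2.4 |
|---|---|---|---|
| same way in both arms | 0 | 0 | 0% |
| in ET only | 0.6 × 0.098 = 0.059 SD (0.25 points) | 0.6 × 0.142 = 0.085 SD (0.37 points) | 10–15% |
| in opposite directions | 0.117 SD (0.50 points) | 0.171 SD (0.73 points) | 21–30% |

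At an assumed 10% loss by Week 4 the values are 0.04–0.06 SD (ET only) and 0.08–0.12 SD (opposite directions).

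**Other working correlations.** These come from a large-sample simulation with a normal outcome, true effect −2.4, SD of change 3.83, 15% loss before Week 4, and dropout log-odds of 1 per SD of baseline (odds ratio about 2.7). Entries are the size of the bias in β06 when dropout depends on baseline in ET only or in opposite directions.

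| True correlation | Independence | Exchangeable | Unstructured |
|---|---|---|---|
| Exchangeable, ρ 0.3–0.7 | 0.13–0.92 (5–39%) | at most 0.04 (under 2%) | at most 0.05 (2%) |
| AR(1), ρ 0.5–0.8 | 0.25–1.28 (11–53%) | 0.07–0.20 (3–8%) | at most 0.065 (under 3%) |

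When the same mechanism applied in both arms, bias was zero to within simulation error (about 0.01) under every structure.

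**Carry-over to the next study.** If the true effect were 2.4 and the bias flattered ET, the ET-only case would give 2.65–2.77. Required sample size goes as 1/effect², so it would be understated by 1 − (2.4/2.65)² = 18% to 1 − (2.4/2.77)² = 25%.

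**The case against.** A reader might infer that GEE is generally biased under MAR, so that β06 is exposed to any ordinary dropout. The documents and the calculation do not support that. β06 is a difference between arms, and the arm biases cancel when the mechanism is the same in both. Bias needs outcome-dependent dropout that differs by arm, together with an independence or misspecified working correlation. The documents give no arm-specific dropout rates or reasons, so differential dropout is plausible, not established.

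A reader might also infer that the plan will use independence. It does not say so, and its wording on autocorrelation leans the other way. That wording does not settle the matter either, since a sandwich variance with an independence structure also accounts for autocorrelation.

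Nor does the plan commit to doing nothing when MAR appears to hold. The same section allows important findings to change later analyses, and dropout related to earlier stigma could be one. What stands against this is that the response would be chosen after seeing the data. The content of the cited procedures could not be checked.

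Finally, efficacy is declared preliminary, and expected attrition is below 15% over the whole follow-up, so loss by Week 4 may be smaller. The ET-only bias of 0.25–0.37 points is 0.29–0.43 of the implied SE of 0.857. This limits the urgency but does not repair the rule, because interpretation is to focus on the size of the effect.

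**Conclusion.** The point holds in a limited form. The rule in step (a) is flawed as written: its condition cannot be checked from the data, and meeting it would not guarantee the stated GEE. With neither a working correlation nor a MAR-valid default named, β06 may be biased if dropout depends on earlier outcomes differently by arm.

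With an independence working correlation, the bias is about 0.06–0.085 SD if only ET dropout depends on baseline. It is 0.12–0.17 SD in the opposite-directions stress case, so about 10–30% of the detectable 2.4 overall. These sizes rest on assumed values: 15% loss by Week 4, correlation 0.6, odds ratios of 2–3 per baseline SD, and an SD solved back from 2.4. Confidence in the fault of principle is high; confidence in the size is not. The sponsor should correct this before analysis.

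**What to change.** Replace the conditional MAR test in step (a) with a prespecified main analysis that is valid under MAR. Either of these would do:

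- a likelihood-based repeated-measures model with the same arm-by-week terms and an unstructured covariance; or
- the planned GEE with an unstructured working correlation, after a simple multiple imputation using arm, baseline and earlier outcomes.

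Keep any imputation model small. With 94/2 = 47 per arm and 15% loss there are about 7 dropouts per arm, and the smallest stratum has 5 planned per arm. Separate imputation by arm with stratum and session attendance would be fragile.

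Add a delta-adjusted MNAR sensitivity analysis for missing Week 4 values: shift the imputed values over a stated range and report how β06 moves. Looking at who drops out and why remains useful as description, but should not decide the method.

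The cost is SAP wording and a little extra work in the Stata or R already planned, with no new data. The downside is reliance on a correctly specified model.

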3.5.4.2 Aim 2: To test the feasibility, acceptability, and preliminary efficacy of the adapted intervention for stigma reduction, we will employ a randomized-controlled design in which we will randomize 80 Thai PLWH to two groups and follow them for 10 weeks.

3.5.4.2.1 Treatment group assignment: We propose to recruit 80 Thai PLWH who will be randomly assigned to either the Enhanced Treatment group (**ET**; $N=40$) or the Treatment-as-Usual group (**TAU**; $N=40$). While the ET group participants will receive the

proposed stigma reduction intervention, the TAU group participants will receive typical services available in the Sanpatong Hospital that are also available to the participants in the

Table 3: Sample Allocation for ET and TAU Groups (# in ET/ # in TAU)

Cisgender Straight Men	Cisgender Straight Women	MSM	Transgender	Substance User
8/8	8/8	10/10	5/5	9/9

ET group, including care co-ordination and linkage to public health nurses in local communities. Using a computer program, we will generate a list of random numbers to assign participants to either group. Numbered envelopes indicating condition assignment will be prepared and sealed. However, to ensure equivalence of gender/sexuality/substance use composition between study arms, we will stratify the sample and randomize each gender/sexuality/substance use category separately, so that each arm will consist of 40 participants with balanced gender/sexuality/substance use compositions. This balanced composition between groups will guarantee sufficient sample sizes for key subpopulations and, hence, enable subsequent analyses for possible heterogeneity of treatment effects. See **Table 3** for the sample allocation for both the ET and TAU groups. Study staff will not be aware of the assignment until the envelope is opened and the baseline survey has been performed.

3.5.4.2.2 Implementation: The stigma reduction intervention will consist of four group counseling sessions delivered by trained interventionists. In each session, a designated interventionist will meet with participants for 120 minutes in a designated room at the Sanpatong Hospital. To help build rapport among the group members, we will host, in total, 5 groups, including 1 group for cisgender straight men who are non-substance users ($n = 8$), 1 group for cisgender straight women who are non-substance users ($n = 8$), 1 group for MSM who are non-substance users ($n = 10$), 1 group for transgender individuals who are non-substance

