3.5.4.2.5 Measurement plans: As in our ongoing studies, structured instruments (see **Table 4**) will be used to assess Thai PLWH regarding their demographics, key clinical characteristics, and psychosocial factors addressed in the intervention, including stigma, attribution styles, physical and emotional arousals, karma beliefs, insights on sufferings, mindfulness, compassion, social support, and care engagement. The psychometric properties have been established for most of the instruments among Asian populations, in particular, in our ongoing R21 project. The survey will be available in the Thai language. The survey will have 250 items in total; however, there are multiple skip patterns. Depending on the responses of Thai PLWH, the survey may have as few as 160 items. These self-report measures will be conducted via Audio Computer-Assisted Self-Interview (ACASI) and will typically be completed within 30-40 minutes. Use of ACASI lessens the likelihood of socially desirable answers and minimizes data entry errors. Similar ACASI survey programs have proven successful in studies of participants with little or no prior computer experience in Asian populations.¹³⁹ Regarding care engagement measures, many studies have used single items to measure ART adherence, for example, gathering categorical data (*yes* or *no*) to measure whether patients achieved 95% adherence. However, in this project, we will create a latent variable for all these items to further control potential measurement errors.^{106,140-142} Viral load (VL) also be collected as an objective measure for adherence. The research staff in charge of data collection will be completely blind to treatment assignments of participants. Please note, our primary outcome is internal stigma, while our secondary outcomes are the indicators for care engagement, including self-reported adherence, viral load, self-reported patient engagement, and clinic visits.

Table 4: Measuring Instruments

Instrument	Items	Instrument description	Cronbach α
Demographic s and clinical outcomes	15	Participants are asked about their age, gender, race, ethnicity, education, income, health insurance, possible HIV transmission route, when they first learned of their HIV diagnosis, opportunistic infections and ART-taking status, morbidity, VL, and current CD4.	
Universal Cognitive-Behavioral components of HIV Stigma			

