HIV stigma (external and internal)	10	The HIV-serostatus subscale of the Multiple Discrimination Scale ³⁰ will be used to measure external HIV stigma . Participants will report whether they experienced 10 different discrimination events in the past year for each of the three discrimination types, including violence, institutional discrimination, and interpersonal discrimination (Yes: 1, and No:0). A summary score will sum across the 10 items. The personalized stigma and negative image subscales of the HIV Stigma Scale ^{31,32,100} will be used to measure internal stigma . The scales ask participants to rank to what extent they agree with 16 statements about HIV stigma in	0.85
	16		> 0.90

		relation to their personhood and self-image (strongly disagree :0 to strong agree : 3). A summary score will be computed to sum across the 16 items.	
Attributions	48	Attribution Style Questionnaire ¹⁴³⁻¹⁴⁵ is a classic measurement to assess individuals' attribution style. This assessment lists 12 good or bad outcomes and probes participants with 4 questions regarding the internality, stability, and globality of these events.	> 0.70
Emotional & physical Reactions	47	The Trait Physiological Hyperarousal Scale ¹⁴⁶ & Dissociation and Arousal subscales of Acute Stress Disorder Scale ^{147,148} will be used to measure participants' perceptions of bodily activation and acute stress reactions (very slightly or not at all : 1 to extremely : 5) during stressful events.	> 0.85
Buddhist Philosophy and Practice			
Karma belief	4	The Fatalistic Karma subscale of the Buddhist COPE Scale ³³ will measure participants' karma belief regarding to what extent they agree that they believe their actions have consequences for themselves and others and that the consequences will occur no matter what they do (strongly disagree :0 to strongly agree : 3)..	0.70
Insights on suffering	52	The Self-Other Four Immeasurable Scale ³⁴ & Nonattachment Scale ¹⁴⁹ will be used to measure participants' insights on suffering through capturing their sense of self, others and their insights into the constructed and impermanent nature of mental representations.	> 0.80
Mindfulness	9	The Cognitive and Affective Mindfulness Scale-Revised ^{35,36} will be used to measure participants' mindfulness practice, including attention, awareness, and acceptance, in their daily lives. (Rarely/Not at all : 1 to Almost always : 4) ¹⁰¹	> 0.75

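### The measurement section makes internal stigma the primary outcome; the analysis plan makes it quality of life and objective health measures, and no quality-of-life instrument is collected

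*Combined protocol and SAP*

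**What the plan says.** Two sections rank the outcomes.

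- **3.5.4.2.5 (Measurement plans):** "our primary outcome is internal stigma, while our secondary outcomes are the indicators for care engagement". The indicators listed are self-reported adherence, viral load, self-reported patient engagement and clinic visits. The same section says "Viral load (VL) also be collected as an objective measure for adherence".
- **3.5.4.2.8.2, step (e):** special attention goes to "our key primary outcome variables (quality of life and objective health measures) as well as secondary outcome variables (stigma, disclosure preparedness". The secondary list continues with family relations, family support, self-management efficacy, adherence, depressive and anxiety symptoms, and physical symptoms. The step adds that every outcome is continuous.

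Table 4 scores two kinds of stigma separately. For external stigma (yes/no items), "A summary score will sum across the 10 items". For internal stigma (items rated 0 to 3), "A summary score will be computed to sum across the 16 items".

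The GEE model in 3.5.4.2.8.2 is fitted separately to each primary or secondary outcome, with β06 (the group difference in change from Week 1 to Week 4) defined as the main between-group effect. Section 3.5.4.2.8.3 gives a detectable β06 of 2.4 at 80% power with N = 80. Neither place names an outcome in the text available; Figure 5, which goes with the power statement, is not shown.

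**The concern.** Step (e) is the only place in the analysis plan that names primary outcomes, and it disagrees with the measurement section. An analyst working from the analysis plan would look for quality-of-life data that no listed instrument supplies, and would report stigma as secondary in a trial whose Aim 2 is to test "preliminary efficacy of the adapted intervention for stigma reduction".

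The plan says that interpretation will rest on effect size, and Aim 3 (3.5.4.3) uses the effect sizes to size the next trial. If the headline outcome is not fixed, neither is the main number the pilot is meant to deliver. Section 3.5.4.2.8.2 also allows later analyses to be modified in light of findings from the preparatory steps. With two conflicting lists on file, either could be cited once the data have been seen.

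**Working it through.** **1. Compare the rankings.**

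| Outcome | 3.5.4.2.5 | Step (e) |
|---|---|---|
| Internal stigma | Primary | Secondary, as unspecified stigma |
| Quality of life | Not listed | Primary |
| Objective health measures | Not listed as such | Primary |
| Viral load | Secondary | Not named; would fall under objective health measures |
| Self-reported adherence | Secondary | Secondary, as adherence |
| Patient engagement, clinic visits | Secondary | Not listed |

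The primary sets {internal stigma} and {quality of life, objective health measures} share 0 entries. Step (e) does not say which stigma score it means. If it meant external stigma only, internal stigma would still not be primary there, so the conflict remains. The viral-load row is an inference, because step (e) does not define objective health measures.

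**2. Check whether Table 4 is complete.** Section 3.5.4.2.5 says "The survey will have 250 items in total". The Table 4 counts, in order, are: demographics and clinical 15, external stigma 10, internal stigma 16, attributions 48, emotional and physical reactions 47, karma belief 4, insights on suffering 52, mindfulness 9, compassion 26, medication adherence 6, 3-day recall 1, 30-day recall 1, Patient Activation Measure 13, clinic visits 2.

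15 + 10 + 16 + 48 + 47 + 4 + 52 + 9 + 26 + 6 + 1 + 1 + 13 + 2 = 250

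This reproduces the stated total exactly, so the listed instruments account for the whole survey and none of the 250 items belongs to a quality-of-life instrument.

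**3. Check what each list can be analysed from.**

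- *3.5.4.2.5:* internal stigma 16 + adherence (6 + 1 + 1 =) 8 + Patient Activation Measure 13 + clinic visits 2 = 39 items, plus viral load. All five outcomes have a data source. Keeping external stigma as well gives 39 + 10 = 49 items.
- *Step (e):* quality of life has no instrument. Objective health measures could be drawn from viral load and CD4. No instrument is named for disclosure preparedness, family relations, family support, or depressive and anxiety symptoms. Self-management efficacy and physical symptoms have no instrument under those names, though existing scales might partly cover them.

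**4. Check whether the power statement settles the matter.** Internal stigma ranges from 0 to 16 × 3 = 48, so if the 2.4 refers to it, 2.4/48 = 5.0% of the range. The text gives no outcome, SD, correlation or alpha. Assuming 40 per arm, two-sided 5% alpha and a normal approximation, 2.4 implies an SD of the Week 1 to Week 4 change of

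2.4 / [(1.96 + 0.84) × √(2/40)] ≈ 3.83

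(4.32 if one-sided). These values do not identify the outcome that was powered.

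**The case against.** The strongest reply is that a reader can resolve the conflict. Section 3.5.4.2.5 is an explicit definition, Aim 2 concerns stigma reduction, and every outcome in that section is collected. Step (e) is one of six preparatory checks. Its family and disclosure items look like carry-over from other work: family-relations wording also appears in 3.5.4.2.8.1 and 3.5.4.2.8.3, and the model text mentions a DT group that this two-arm design does not have. The study is openly not powered for efficacy, and no sample-size figure is shown to depend on the ranking.

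Much of this stands. It makes internal stigma the likelier intention, although the carry-over explanation is inference. It does not remove the conflict: the analysis plan still names a different primary, one part of it unmeasured, and nothing later overrides it.

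Two narrower objections also have force. In the model section, calling β06 the main effect picks out the Week 4 contrast from β07 and β08, and generic outcome notation is normal there. The fault is therefore in the outcome ranking, not the model. And since Figure 5 is not shown, it may label the scale of the 2.4; that point is conditional and carries no weight in the conclusion.

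**Conclusion.** The concern holds and must be fixed. The two sections name different primary outcomes, with 0 in common, and one step (e) primary has 0 of 250 survey items behind it. This is a contradiction in the current text, not missing detail. It rests on Table 4 being the full instrument list, which the exact sum to 250 supports.

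The practical harm is bounded. In a pilot that interprets magnitude, it is mainly ambiguity over which effect size is the headline result and is carried into planning the next trial. The explicit demotion is that of stigma; the change in rank of viral load depends on how objective health measures is read.

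**What to change.** Subject to sponsor confirmation, and before any unblinded analysis:

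1. Replace the outcome list in step (e) with that of 3.5.4.2.5. **Primary:** internal stigma summary score (16 items, 0–48), treatment effect β06 at Week 4. **Secondary:** self-reported adherence, viral load, Patient Activation Measure score, clinic visits.
2. If external stigma (10 items, 0–10) is wanted, list it separately as secondary or exploratory.
3. Remove the step (e) outcomes with no instrument. For self-management efficacy and physical symptoms, either name the Table 4 scale that measures each or drop them.
4. Delete the remark that all outcomes are continuous, since missed and delayed visits are counts. The model's link function already allows for this.
5. Name the outcome and scale for the main β06 and for the 2.4 in 3.5.4.2.8.3.

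This costs wording only, because every outcome in items 1 and 2 is already collected. If quality of life is the intended primary, add an instrument to the 250-item survey before baseline and correct 3.5.4.2.5 instead.

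Two separate, minor discrepancies can be reconciled in the same edit. Section 3.5.4.2.6 places the dried blood spot at Weeks 1 and 4, while Table 5 shows viral load at Weeks 1, 4, 7 and 10. Section 3.5.4.2.5 says the survey covers "insights on sufferings, mindfulness, compassion, social support, and care engagement", but Table 4 has no social-support row.
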